4.2.2.1.2 Safety Analysis Set

The primary endpoint of ORR as assessed by the investigator per RECIST 1.1 in patients treated with savolitinib 300 mg od + osimertinib in FISH5+ and/or IHC50+ who have progressed following treatment with osimertinib will be summarised using the SAF.

The ORR and its 2-sided 95% CI (Clopper-Pearson) will be summarised and will be analysed using an exact binomial test against the null H_0 : ORR=30% at the significance level of $\alpha=0.05$. Summaries will be produced that present the number and percentage of patients with a tumour response (CR/PR).

BoR will also be presented and summarised by n (%) for each category (CR, PR, SD, PD and NE).

4.2.2.2 Secondary Endpoint - Objective Response Rate

4.2.2.2.1 Contribution of Components Analysis Set

To describe the difference in the efficacy of savolitinib (300 mg bid) in combination with osimertinib and savolitinib (300 mg bid) in combination with placebo in patients with EGFRm+, MET amplified/overexpressed (FISH10+ and/or IHC90+), locally advanced or metastatic Non-Small Cell Lung Cancer [NSCLC] who have progressed following treatment with 1L osimertinib therapy under CSP version 7.0, ORR (as assessed by the investigator per RECIST 1.1) with 95% confidence intervals (Clopper-Pearson) will be constructed in the CAS for:

- 300 mg bid (savolitinib) + osimertinib
- 300 mg bid (savolitinib) + placebo.

BoR will also be presented and summarised by n (%) for each category (CR, PR, SD, PD and NE).

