3 OBJECTIVES AND ENDPOINTS

Table 4 Study objectives

Primary Objective:	Endpoint:

• To determine the efficacy of savolitinib (300 mg bid) in combination with osimertinib in patients with EGFRm+ and MET amplified/overexpressed (FISH10+ and/or IHC90+)^a, locally advanced or metastatic NSCLC who have progressed following treatment with 1L osimertinib• To determine the efficacy of savolitinib (300 mg od) in combination with osimertinib in patients with EGFRm+, MET amplified/overexpressed (FISH5+ and/or IHC50+)^b, locally advanced or metastatic NSCLC who have progressed following osimertinib.	
• ORR by investigator assessment in accordance with RECIST 1.1.
Secondary Objectives:	Endpoints:
To determine the efficacy of savolitinib (300 mg bid) in combination with osimertinib in patients with EGFRm+ and MET amplified/overexpressed (FISH10+ and/or IHC90+) ^a , locally advanced or metastatic NSCLC who have progressed following treatment with 1L osimertinib.	
• DoR and PFS by investigator assessment in accordance with RECIST 1.1• OS
To describe the difference in the efficacy of savolitinib (300 mg bid) in combination with osimertinib and savolitinib (300 mg bid) in combination with placebo in patients with EGFRm+, MET amplified/overexpressed (FISH10+ and/or IHC90+) ^a , locally advanced or metastatic NSCLC who have progressed following treatment with 1L osimertinib therapy under CSP version 7.0.	
• ORR by investigator assessment in accordance with RECIST 1.1
To determine the efficacy of savolitinib (300 mg od and 600 mg od, respectively) in combination with	
• ORR, DoR, and PFS, by investigator assessment in accordance with RECIST 1.1.

osimertinib in patients with EGFRm+, MET-amplified/overexpressed (FISH10+ and/or IHC90+)^a, locally advanced or metastatic NSCLC who have progressed following treatment with 1L osimertinib.
	
 • OS

To determine the efficacy of savolitinib (300 mg od, 300 mg bid, and 600 mg od, respectively) in combination with osimertinib in patients with EGFRm+, MET-amplified/overexpressed (FISH10+ and/or IHC90+)^a, locally advanced or metastatic NSCLC who have progressed following treatment of \geq 2L osimertinib.
	
 • ORR, DoR, and PFS, by investigator assessment in accordance with RECIST 1.1. • OS

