Under CSP version 5.0, approximately **CCI** patients (post 1L or 2L osimertinib) were planned to be randomised in a **CCI** ratio to receive osimertinib 80 mg od in combination with either savolitinib 300 mg bid (approximately **CCI** patients) or savolitinib 600 mg od (approximately **CCI** patients). Since **CCI** patients had already received the 600 mg od dose (enrolled prior to CSP version 5.0, under the previous weight-based dosing schedule), approximately **CCI** patients in total were planned to receive osimertinib in combination with savolitinib 600 mg od. Under CSP version 6.0, the enrolment was further restricted to post 1L osimertinib and central MET FISH+ only, therefore approximately **CCI** patients that were planned to be randomised in a **CCI** ratio to osimertinib 80mg od in combination with either savolitinib 300 mg bid or savolitinib 600 mg od applied to the new population (ie, post 1L osimertinib and central MET FISH+).

Under CSP version 7.0, approximately **CCI** patients (post 1L osimertinib with MET amplification/overexpression [FISH10+ and/or IHC90+]) will be randomised in a **CCI** ratio to receive savolitinib 300 mg bid + osimertinib 80 mg (approximately **CCI** patients) or savolitinib 300 mg bid + placebo to osimertinib (approximately **CCI** patients). With assumed ORRs of 55% and **CCI**%, for the savolitinib 300 mg bid + osimertinib 80 mg and the savolitinib 300 mg bid + placebo arms respectively, there will be at least **CCI**% power at a 2-sided 0.05 significance level to detect a difference in ORRs of the 2 arms.

Approximately **CCI** to **CCI** patients are anticipated to be pre-screened for MET-amplified/overexpressed status in this study.

Primary and final analyses:

For the savolitinib 300 mg bid dosing regimen, with approximately **CCI** patients (approximately **CCI** patients under CSP version 7.0 and approximately **CCI** patients under CSP version 5.0 and version 6.0) with FISH10+ and/or IHC90+ status who have progressed following 1L osimertinib treatment, CIs will be provided and be compared with the historical reference platinum-pemetrexed chemotherapy ORR of approximately **CCI**%.

For the savolitinib 300 mg od dosing regimen, with approximately **CCI** patients with FISH5+ and/or IHC50+ status who have progressed following osimertinib treatment, there will be at least **CCI**% power for an exact binomial test with a 2-sided significance level of 0.05 to detect a

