9.4.3.2 Analysis of the secondary endpoints

Analyses for the efficacy secondary endpoints will be summarised using the TPAS, CAS, and SAF datasets (see Section 9.3 for analysis set definitions).

Objective response rate

To describe the difference in the efficacy of savolitinib (300 mg bid) in combination with osimertinib and savolitinib (300 mg bid) in combination with placebo in patients with EGFRm+, MET amplified/overexpressed (FISH10+ and/or IHC90+), locally advanced or metastatic NSCLC who have progressed following treatment with 1L osimertinib therapy under CSP version 7.0, ORR with 95% confidence intervals will be constructed in the CAS for:

- Osimertinib + savolitinib (300 mg bid)
- Placebo to osimertinib + savolitinib (300 mg bid)

Additional details for the analysis of ORR on other dosing regimen/lines of therapy/biomarker population will be specified in the SAP.

Duration of response

The DoR will be defined as the time from the date of first documented response until date of documented progression or death in the absence of disease progression (ie, date of PFS event or censoring—date of first response+1). The end of response should coincide with the date of progression or death from any cause used for the PFS endpoint. The time of the initial response will be defined as the latest of the dates contributing towards the first visit response of CR or PR.

If a patient does not progress following a response, then their DoR will use the respective PFS censoring time.

If there are sufficient numbers of responders, and sufficient numbers of responses that have progressed by the point of the analysis, Kaplan-Meier plots of DoR in the responding patients will be produced and appropriate descriptive summary statistics will be presented (n, number of responses that have progressed, median, quartile, minimum and maximum DoR).

Progression-free survival

PFS is defined as the time from randomisation (patients recruited under CSP version 7.0) or start of treatment (patients recruited prior to CSP version 7.0) until the date of objective disease progression or death (by any cause in the absence of progression) regardless of whether the patient withdraws from therapy or receives another anti-cancer therapy prior to progression. Patients who have not progressed or died at the time of analysis will be censored at the time of the latest date of assessment from their last evaluable RECIST assessment.

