under the previous weight- based dosing schedule), approximately **[CC1]** patients in total were planned to receive osimertinib in combination with savolitinib 600 mg od.

Under CSP version 6.0, the enrolment was further restricted to post 1L osimertinib and central MET FISH+ only, therefore approximately **[CC1]** patients that were planned to be randomised in a 2:1 ratio to osimertinib 80mg od in combination with either savolitinib 300 mg bid or savolitinib 600 mg od applied to the new population (ie, post 1L osimertinib and central MET FISH+).

Under CSP version 7.0, approximately **[CC1]** patients (post 1L osimertinib with MET amplification/overexpression [FISH10+ and/or IHC90+] will be randomised in a 2:1 ratio to receive savolitinib 300 mg bid + osimertinib 80 mg (approximately **[CC1]** patients) or savolitinib 300 mg bid + placebo to osimertinib (approximately **[CC1]** patients). With assumed objective response rates [ORRs] of

CCI and CCI, for the savolitinib 300 mg bid + osimertinib 80 mg and the savolitinib 300 mg bid + placebo arms respectively, there will be at least CCI power at a 2-sided 0.05 significance level to detect a difference in ORRs of the 2 arms.

Overall, approximately CCI to CCI patients are anticipated to be pre-screened for MET-amplified/overexpressed status in this study.

All patients confirmed as eligible will begin treatment on Day 1 with osimertinib + savolitinib combination therapy or placebo to osimertinib + savolitinib. Treatment will continue in 28-day cycles until objective disease progression by investigator per Response Evaluation Criteria in Solid Tumours [RECIST] 1.1 is assessed, unacceptable toxicity, withdrawal of consent or another discontinuation criterion is met.

Under CSP version 7.0 only, at investigator-assessed progressive disease [PD] per RECIST 1.1, treatment allocation will be unblinded and those patients randomised to the savolitinib plus placebo arm will have the opportunity to cross over to the savolitinib plus osimertinib regimen.

To be noted, all patients treated with savolitinib 300 mg od or 600 mg od indiscriminately of CSP versions will be analysed all together (e.g. all 300 mg od or all 600 mg od, respectively).

Primary and final analyses:

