3.1.2 Stratification factor(s)

There is one stratification factor of baseline brain metastases (Yes/No) introduced for patients randomised under CSP version 7.0. When necessary, and only for patients belonging to CAS, the stratification in the statistical analyses will be based on the baseline brain scan assessed by the investigator using the values entered in the IWRS at randomisation, even if it is subsequently discovered that these values were incorrect.

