4.2.2.2.3 Secondary Endpoint of ORR based on BICR

Summaries will also be produced for ORR assessed by BICR using the TPAS, SAF and CAS.

In detail, for SAF:

- savolitinib (300 mg od, 300 mg bid and 600 mg od, respectively) in combination with osimertinib in patients with EGFRm+, MET amplified/overexpressed (FISH10+ and/or IHC90+), locally advanced or metastatic NSCLC who have progressed following osimertinib
- savolitinib (300 mg od, 300 mg bid and 600 mg od, respectively) in combination with osimertinib in patients with EGFRm+, MET amplified/overexpressed (FISH5+ and/or IHC50+), locally advanced or metastatic NSCLC who have progressed following osimertinib.

Finally, summaries will be produced using the CAS for:

- 300 mg bid (savolitinib) + osimertinib
- 300 mg bid (savolitinib) + placebo.

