4.2.2.4.3 Contribution of Components Analysis Set

PFS will be summarised using the Kaplan-Meier methodology and will be based on CAS for:

- 300 mg bid (savolitinib) + osimertinib
- 300 mg bid (savolitinib) + placebo.

Median time to progression, and quartiles will be summarised, including 95% CI. The percentage of patients being progression-free at 3, 6, 9, 12, 18, 24, 30 and 36 months, along with the 95% CI, and the median and range of duration of follow-up in censored patients, will also be presented. Kaplan Meier curves will also be plotted.

PFS will be analysed using a stratified log-rank test adjusting for the stratification used in randomisation for the generation of the p-value. The effect of treatment will be estimated by the HR together with its corresponding 95% CI for the CAS. An HR less than 1 will favour savolitinib plus osimertinib. The HR and its CI will be estimated from a Cox Proportional Hazards model (with ties = Efron and baseline stratification) and the CI calculated using a profile likelihood approach. If there are insufficient events per strata, a log-rank test will be used to analyse PFS instead of a stratified log-rank test.

Treatment status at time of progression will be presented, showing patients who were on savolitinib and/or osimertinib at time of progression and patients who discontinued treatment prior to progression.

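### The randomised ORR comparison has a power statement but is reported only as one interval per arm, with no interval for the difference and no use of the stratum; BICR PFS also drops the randomised set

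*SAP*

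**What the plan says.** The version 7.0 objective in Protocol section 3 reads "To describe the difference in the efficacy of savolitinib (300 mg bid) in combination with osimertinib and savolitinib" plus placebo, with investigator ORR as its only endpoint. Protocol 9.2 gives the cohort "power at a 2-sided 0.05 significance level to detect a difference in ORRs of the 2 arms", and SAP 2.1 repeats the statement: "to detect a difference in ORRs of the 2 arms".

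The analysis sections are narrower. Protocol 9.4.3.2 says "ORR with 95% confidence intervals will be constructed in the CAS for" the two arms, listed one by one. SAP 4.2.2.2.1 follows it and adds only the interval method: "ORR (as assessed by the investigator per RECIST 1.1) with 95% confidence intervals (Clopper-Pearson) will be constructed in the CAS for" the same two arms, plus best objective response by category.

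On stratification, SAP 3.1.2 says "When necessary, and only for patients belonging to CAS, the stratification in the statistical analyses will be based on the baseline brain scan". The one CAS analysis that names the stratum is investigator PFS (SAP 4.2.2.4.3): "PFS will be analysed using a stratified log-rank test adjusting for the stratification used in randomisation", with a Cox hazard ratio.

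For central review, SAP 4.2.2.2.3 states "Summaries will also be produced for ORR assessed by BICR using the TPAS, SAF and CAS", and SAP 4.2.2.3.4 names the same three sets for DoR. SAP 4.2.2.4.4, on BICR PFS, names only the TPAS and SAF.

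**The concern.** Version 7.0 added randomisation so that the combination could be set against savolitinib alone. ORR is the endpoint of that objective and the one for which power is stated. A reader of the planned output gets two response rates with their own intervals and can subtract one rate from the other, but is not told how precisely the difference is known. Two separate intervals are a poor guide to that. If the interval for the difference is added later, its method and the handling of the stratum will be chosen after the data have been seen.

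The power sentence is also left without a matching analysis. It presupposes a two-sided 0.05 comparison, none is planned for ORR, and neither document says the figure is for planning only.

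The BICR PFS point is a separate defect. The SAP gives its programmer two incompatible instructions on whether to produce BICR PFS for the randomised arms.

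**Working it through.** **The plan's own figure.** The stated power cannot be reproduced, because the power, the arm sizes and the monotherapy ORR are all redacted. Three inputs are readable: combination ORR 55% (Protocol 9.2), two-sided alpha 0.05 (Protocol 9.2, SAP 2.1) and 2:1 allocation (Protocol 1.2, SAP 2.1). Everything below assumes arms of 40:20, 60:30 or 80:40 and a monotherapy ORR of 15, 20, 25 or 30%.

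**One table.** Take 22/40 (55%) against 4/20 (20%).

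- Planned output: Clopper-Pearson 38.5–70.7% and 5.7–43.7%. These overlap.
- Difference: 0.55 − 0.20 = 0.35. Newcombe's interval uses the Wilson limits of each arm, here 0.3983–0.6929 and 0.0807–0.4160.
  - Lower: 0.35 − √[(0.55 − 0.3983)² + (0.4160 − 0.20)²] = 0.35 − 0.264 = 0.086.
  - Upper: 0.35 + √[(0.6929 − 0.55)² + (0.20 − 0.0807)²] = 0.35 + 0.186 = 0.536.
- So the difference is 35 points, 95% CI 8.6 to 53.6.

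**Over the assumed range.** Both binomials were enumerated exactly, with the combination at 55%. Each cell lists the results for monotherapy ORR 15 / 20 / 25 / 30%.

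| Arms | Expected width of 95% CI for the difference (points) | Chi-square power, % | Two arm CIs do not overlap, % | Difference CI excludes 0 while arm CIs overlap, % |
|---|---|---|---|---|
| 40:20 | 43 / 44 / 46 / 47 | 89 / 78 / 63 / 47 | 54 / 35 / 21 / 12 | 35 / 42 / 41 / 35 |
| 60:30 | 35 / 37 / 38 / 39 | 98 / 91 / 79 / 61 | 82 / 62 / 42 / 24 | 16 / 29 / 37 / 37 |
| 80:40 | 31 / 32 / 33 / 34 | 99.5 / 97 / 89 / 74 | 94 / 81 / 60 / 38 | 5 / 16 / 29 / 37 |

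The plan states no overlap rule, so the last two columns do not measure an error rate of this trial. They show only how loosely two arm intervals track the contrast. The gap is small when arms are large and the monotherapy ORR is low: 99.5% against 94.4% at 80:40 with 15%. A stratified interval cannot be illustrated, because the documents give no stratum sizes or rates.

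**Where a contrast might be found.**

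| CAS analysis | Planned output | Between-arm estimate | Stratum used |
|---|---|---|---|
| Investigator ORR (SAP 4.2.2.2.1) | By arm | None | No |
| BICR ORR (SAP 4.2.2.2.3) | By arm | None | No |
| ORR by retrospective IUO MET status (SAP 4.2.2.14.1.4) | By arm | None | No |
| Investigator PFS (SAP 4.2.2.4.3) | By arm, test, HR | Yes | Yes |

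**BICR PFS.** Part (3) of the BICR objective in Protocol section 3 asks for ORR, DoR and PFS in both version 7.0 arms. The matching row of SAP Table 3 lists the CAS for all three. The BICR ORR and DoR sections include the CAS; the PFS section does not. SAP section 6 lists other departures from the protocol but not this one. The only BICR PFS planned in the CAS is exploratory CNS PFS in patients with baseline CNS metastases (SAP 4.2.2.9.1).

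**The case against.** The objective is to describe, Protocol 9.1 states no hypothesis for this comparison, and the SAP does what Protocol 9.4.3.2 asks. Where the authors wanted a comparative analysis, as for PFS, they wrote one. That stands: a missing p-value is not an error, and on ORR the two documents agree with each other. But describing a difference includes giving its precision, and the power sentence still needs either an analysis or a label.

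Responder counts by arm will be reported, so a reader could compute an unstratified interval such as the one above. That also stands. The counts do not give a stratified interval, and they do not fix the method in advance.

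SAP 3.1.2 uses the stratum only where necessary, so leaving it out breaks no rule. This is true. Stratifying the ORR difference is good practice with a factor already in hand, not the correction of a breach.

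The sizes are scenarios, since the key inputs are redacted. This is accepted. The finding itself rests on the text and not on those figures.

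The BICR PFS omission may be a one-line slip, because the SAP's amendment history says section 4 was updated to match Table 3. That is plausible, but as written the two parts of the SAP still conflict.

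**Conclusion.** The point holds in all its parts. For ORR in the CAS, neither document plans a between-arm estimate with an interval, although the objective is that difference and power is stated for it. This is a low-cost improvement to the plan more than an outright error. Under the assumed arm sizes and monotherapy rates, the unreported interval would be roughly 31 to 47 points wide, which is wide enough to matter for how the contribution of osimertinib is read. The absence of the CAS from BICR PFS is wrong as written: it conflicts with the protocol objective and with SAP Table 3, and it is not declared. Neither part affects the two primary endpoints.

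**What to change.** 1. In Protocol 9.4.3.2 and SAP 4.2.2.2.1, add the CAS difference in ORR (combination minus savolitinib + placebo) with a 95% CI, stratified by the IWRS value for baseline brain metastases. Mantel-Haenszel weights would do, with a stated rule for pooling sparse strata. Repeat it for BICR ORR in SAP 4.2.2.2.3.
2. Either add the matching two-sided 0.05 Cochran-Mantel-Haenszel test as a secondary analysis with no multiplicity claim, or say in Protocol 9.2 and SAP 2.1 that the power figure is for planning only.
3. State that, if the savolitinib + placebo arm closes for futility, the difference is limited to concurrently randomised patients. SAP section 5 lets recruitment to the combination arm continue alone in that case, and the CAS definition does not say how those later patients are handled.
4. In SAP 4.2.2.4.4, restore BICR PFS by arm in the CAS, or declare and justify the omission in SAP section 6. A stratified hazard ratio for BICR PFS would be an optional extra beyond the protocol.

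The cost is protocol and SAP wording and a few tables, with no new data or patients.

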4.2.2.2.2 Safety Analysis Set

The secondary endpoints of ORR as assessed by the investigator per RECIST 1.1 will be summarised using the SAF for:

- savolitinib (300 mg od and 600 mg od, respectively) in combination with osimertinib in patients with EGFRm+, MET amplified/overexpressed (FISH10+ and/or IHC90+), locally advanced or

metastatic NSCLC who have progressed following treatment with 1L osimertinib

- savolitinib (300 mg od, 300 mg bid and 600 mg od, respectively) in combination with osimertinib in patients with EGFRm+, MET amplified/overexpressed (FISH10+ and/or IHC90+), locally advanced or metastatic NSCLC who have progressed following treatment with >=2L osimertinib
- savolitinib (300 mg bid and 600 mg od, respectively) in combination with osimertinib in patients with EGFRm+, MET amplified/overexpressed (FISH5+ and/or IHC50+), locally advanced or metastatic NSCLC who have progressed following osimertinib.

4.2.2.2.1 Subgroup analyses

Subgroups analyses of ORR, as assessed by the investigator per RECIST 1.1, in SAF patients treated with savolitinib 300 mg od in combination with osimertinib with EGFRm+, MET amplified/overexpressed (FISH10+ and/or IHC90+), will be conducted within the following subgroups (Appendix “A”):

- Race [Asian, Non-Asian]
- Sex [Male, Female]
- Age at baseline [<65 years, \geq 65 years]
- Line of treatment [2nd line, \geq 3rd line]. Line of treatment is equal to the number of regimens of previous anti-cancer therapies in metastatic setting at baseline + 1. Therefore, line of treatment = ‘2nd line’ directly refers to the number of regimens of previous anti-cancer therapies at baseline = 1. As such line of treatment = ‘ \geq 3rd line’ is a combination of patients with the number of regimens of previous anti-cancer therapies at baseline = 2 or 3 or more. The number of regimens of previous anti-cancer therapies at baseline will be identified by an AstraZeneca medically qualified expert during the medical review process
- Prior platinum-based chemotherapy [Yes, No] in metastatic setting. This classification will be identified by an AstraZeneca medically qualified expert during the medical review process
- Prior platinum-based chemotherapy and line of treatment [Yes and 2nd line, Yes and \geq 3rd line, No and 2nd line, No and \geq 3rd line’]
- Immediately prior line of therapy [Osimertinib, Prior platinum-based chemotherapy, Other]. This classification will be identified by an AstraZeneca medically qualified expert during the medical review process
- Response to immediately prior line of therapy [Yes and osimertinib, Yes and platinum-based chemotherapy, Yes and other, No and osimertinib, No and platinum-based chemotherapy, . No and other]. Response is defined as Best Response (complete or partial), as reported by the investigator and it will be identified by an AstraZeneca medically qualified expert during

the medical review process

- Immediately prior line osimertinib [Osimertinib, Not osimertinib]. This classification will be identified by an AstraZeneca medically qualified expert during the medical review process
- Response to immediately prior line of therapy, osimertinib [Yes and osimertinib, Yes and not osimertinib, No and osimertinib, No and not osimertinib]. Response is defined as Best Response (complete or partial), as reported by the investigator and it will be identified by an AstraZeneca medically qualified expert during the medical review process
- Number of previous EGFR Tyrosine kinase inhibitor [TKI] therapies [1, 2, ...]. Where possible, EGFR TKI therapies will be identified programmatically, otherwise they will be identified by an AstraZeneca medically qualified expert during the medical review process
- T790M status in baseline plasma [T790M+, T790M-]
- C797S mutation in baseline plasma (C797S+, C797S-)
- FISH+ allocation status [Amplified, Polysomy]. Patients can be considered FISH+ by either amplification or polysomy, where amplification is considered a ratio of 'Mean MET/CEP7 RATIO' or 'CEP7/MET RATIO' ≥ 2 and polysomy where ratio < 2 . The non-FISH+ patients will be excluded. Ratio information will be provided by external vendors
- IHC+ allocation status [IHC90+, IHC90 negative (FISH10+), IHC50+, IHC50 negative (FISH5+), IHC missing/unknown (FISH+ to enter study)]
- FISH+ allocation status [FISH10+, FISH10 negative (IHC90+), FISH5+, FISH5 negative (IHC50+), FISH missing/unknown (IHC+ to enter study)]
- Overall disease classification [Metastatic, Locally advanced, Missing].
- EGFR mutation status [Exon 19 deletion, L858R]
- Known or treated brain metastases at study entry [Yes (present at baseline or not present at baseline but with known or treated history of brain metastases), No (not present at baseline and not known or treated history of brain metastases)]. This classification will be identified by an AstraZeneca medically qualified expert during the medical review process
- ECOG at baseline [0, 1, ...]
- Histological Type [Adenocarcinoma, Other].

Forest plots of ORR with 95% Clopper-Pearson CI for each subgroup will also be produced.

